12.6	Public disclosure and publication policy.....	35
13.	STRUCTURED RISK ANALYSIS.....	35
14.	REFERENCES	35
	Table 1.....	37
	Table 2.....	38
	Table 3	39
	Table 4.....	39
	Figure 1.....	40
	Appendix 1.....	41
	Appendix 2	43

LIST OF ABBREVIATIONS AND RELEVANT DEFINITIONS

ABR	ABR form, General Assessment and Registration form, is the application form that is required for submission to the accredited Ethics Committee (In Dutch, ABR = Algemene Beoordeling en Registratie)
AE	Adverse Event
AR	Adverse Reaction
CA	Competent Authority
CCMO	Central Committee on Research Involving Human Subjects; in Dutch: Centrale Commissie Mensgebonden Onderzoek
CV	Curriculum Vitae
DSMB	Data Safety Monitoring Board
EU	European Union
EudraCT	European drug regulatory affairs Clinical Trials
GCP	Good Clinical Practice
IB	Investigator's Brochure
IC	Informed Consent
IMP	Investigational Medicinal Product
IMPD	Investigational Medicinal Product Dossier
LDN	Laparoscopic Donor Nephrectomy
LUMC	Leids Universitair Medisch Centrum
METC	Medical research ethics committee (MREC); in Dutch: medisch ethische toetsing commissie (METC)
NMB	Neuromuscular Block
PNP	Pneumoperitoneum
POD	Post Operative Day
PTC	Post Tetanic Count
QOR	Quality of Recovery
RCT	Randomized Controlled Trial
(S)AE	(Serious) Adverse Event
SPC	Summary of Product Characteristics (in Dutch: officiële productinformatie IB1-tekst)
Sponsor	The sponsor is the party that commissions the organisation or performance of the research, for example a pharmaceutical company, academic hospital, scientific organisation or investigator. A party that provides funding for a study but does not commission it is not

regarded as the sponsor, but referred to as a subsidising party.

SRS **Surgical Rating Scale**

SUSAR **Suspected Unexpected Serious Adverse Reaction**

TOF **Train of Four (measurement)**

Wbp **Personal Data Protection Act (in Dutch: Wet Bescherming Persoonsgegevens)**

WMO **Medical Research Involving Human Subjects Act (in Dutch: Wet Medisch-wetenschappelijk Onderzoek met Mensen)**

SUMMARY

Rationale: As both patients with end-stage kidney disease as society benefit tremendously from living kidney donors, their safety and well-being are highly important objectives in living kidney donation. In this randomized controlled clinical trial we will compare the use of deep neuromuscular blockade versus moderate neuromuscular blockade – with standard pressure pneumoperitoneum – during laparoscopic donor nephrectomy.

Objective: To establish the relationship between the use of deep neuromuscular blockade (NMB) during laparoscopic donor nephrectomy (LDN) - with standard pressure pneumoperitoneum (PNP) - and the early quality of recovery.

Study design: A multi-center, blinded, randomized controlled clinical trial.

Study population: Adult individuals who are scheduled for living kidney donation are eligible for this study. All types of donors, including related, unrelated, anonymous and donors who participate in the “cross-over” exchange program are eligible.

Intervention: 2 treatment groups:

- deep neuromuscular blockade and standard pressure pneumoperitoneum
- moderate neuromuscular blockade and standard pressure pneumoperitoneum

Main study endpoint: Quality of recovery score (QOR-40 questionnaire) at 24 hours after extubation.

Nature and extent of the burden and risks associated with participation, benefit and group relatedness:

The burden for participants in this study is mainly related to the evaluation of the endpoints during the early postoperative phase. Assessment of the differential pain scores and the QOR-40 questionnaire will take approximately 10 minutes per time-point (-18h, 1h, 6h, 24h and 48h after detubation). As the use of a deep NMB with a standard insufflations pressure improves the quality of the surgical field, there are no risks related to the surgery. A deep neuromuscular block can be achieved by higher doses of rocuronium as compared to the routine intubation dose. A higher dose of rocuronium in living kidney donors is safe, as renal function is only slightly reduced which does not have a clinically relevant impact on the clearance of rocuronium.

To overcome the extended effects of deep neuromuscular blockade that may lead to airway obstruction, hypoxia, pneumonia and/or atelectasis, sugammadex is administered to antagonize the effects of rocuronium. Sugammadex is a rapid antagonist of neuromuscular blockade by rocuronium that is given immediately after surgery. Randomized controlled trials have shown that sugammadex can be safely administered in patients, without dose adjustments for young, elderly or obese patients and that it can also be safely administered in patients with suboptimal renal function.

A recent study performed by Martini *et al.* has shown that deep neuromuscular blockade improves surgical conditions with reduced postoperative pain scores after laparoscopic surgery (1). Moreover, preliminary data of our recently performed Leopard-3 study, show that the mean SRS (surgical rating scale) was significantly better during deep NMB with less opiate consumption (2). Altogether, we expect that the use of deep NMB during LDN reduces postoperative pain scores and/or analgesia consumption. This may improve the early quality of recovery of living kidney donors.

1. INTRODUCTION AND RATIONALE

In our previous pilot study (*acronym: Leopard-1 study*) low-pressure pneumoperitoneum during LDN reduced postoperative pain scores as compared to standard pressure pneumoperitoneum (3). This finding is in line with our recent meta-analysis which shows that the use of low-pressure pneumoperitoneum (7 mmHg) provides a clinically relevant reduction in postoperative pain scores after laparoscopic surgery (4). Despite this evidence and the fact that international consensus guidelines state that the lowest possible intra-abdominal pressure should be used during laparoscopic procedures (5, 6), almost all laparoscopic surgeons use a fixed standard insufflation pressure (10-15 mmHg) instead of the lowest possible pressure (<10 mmHg). In our view, the main reason for this is that low-pressure PNP may compromise the quality of the surgical field.

Staeher-Rye *et al.* showed that the use of a deep NMB improves surgical conditions during low-pressure PNP laparoscopy as compared to a moderate NMB (7). To investigate whether the use of low-pressure PNP facilitated by profound muscle relaxation not only improves postoperative pain but also the early quality of recovery, we performed a blinded RCT in patients undergoing LDN (*Leopard-2 study; NCT02146417*) (8, 9). Results from this study show that live kidney donors allocated to the low-pressure group mobilized earlier and were sooner physically independent. This led to a remarkably shorter length of hospital stay. In the low-pressure group, 45% of live kidney donors went home at postoperative day 2 as compared to 20% in the standard-pressure group. However, patients in the low-pressure group did not have lower overall pain scores, nor reduced analgesia consumption (9).

We recently completed a randomized controlled study (*Leopard-3 study*) in which low-pressure PNP was used and the intra-abdominal pressure was increased step-wise in case of insufficient surgical conditions during LDN (2). Preliminary data show that the use of a deep NMB led to a mean intra-abdominal pressure of 7.5 mmHg, whereas a mean pressure of 9 mmHg was required to achieve sufficient conditions with a moderate NMB (paper in preparation). Moreover, the mean SRS score was significantly better in during deep NMB. In our view this shows that a step-wise approach combined with deep NMB enables the use of low-pressure PNP without compromising the quality of the surgical field during laparoscopic procedures. Interestingly, we also observed a reduced cumulative opiate consumption during the first 24 hours after surgery in the deep NMB group. In our view, this finding could not be attributed to the slight difference in mean intra-abdominal pressure (7.5 *versus* 9 mmHg). Therefore, this observation appears to contradict the results from the Leopard-2 study in which no difference was found between low- and standard pressure PNP with regard to

postoperative pain and analgesia use (please see table 1). However, results from both studies could be brought in line if the use of deep NMB independently reduces postoperative pain after laparoscopy. Therefore we hypothesize that the use of a deep NMB during LDN with standard pressure PNP (12 mmHg) reduces postoperative pain scores and/or analgesia consumption which leads to an improved early quality of recovery.

2. OBJECTIVES

Primary Objective:

To establish the relationship between the use of deep neuromuscular blockade (NMB) during laparoscopic donor nephrectomy (LDN) -with standard pressure pneumoperitoneum of 12 mmHg- and the early quality of recovery.

Secondary Objective:

To study whether deep NMB during LDN influences postoperative pain and/or analgesia consumption.

3. STUDY DESIGN

Study design and duration:

A multi-center, blinded, randomized controlled clinical trial.

A multicenter design was chosen to optimize generalizability and to guarantee patient enrollment within 12 months.

Participating centers:

- Radboudumc, Nijmegen ([name], surgeon and [name], anesthesiologist)
- LUMC, Leiden ([name], surgeon and [name], anesthesiologist)

4. STUDY POPULATION

4.1 Population

Adult individuals who are scheduled for live kidney donation are eligible for this study. All types of donors, including related, unrelated, anonymous and donors who participate in the “cross-over” exchange program are eligible.

4.2 Inclusion criteria

In order to be eligible to participate in this study, a subject must meet all of the following criteria:

- obtained informed consent
- age over 18 years

4.3 Exclusion criteria

A potential subject who meets any of the following criteria will be excluded from participation in this study:

- insufficient control of the Dutch language to read the patient information and to fill out the questionnaires
- chronic use of analgesics or psychotropic drugs
- use of NSAIDs shorter than 5 days before surgery
- known or suspect allergy to rocuronium or sugammadex
- neuromuscular disease
- indication for rapid sequence induction
- deficiency of vitamin K-dependent clotting factors, coagulopathy or use of coumarin derivatives.
- Peri-operative use of fusidic acid or flucloxacillin
- Severe renal impairment (creatinine clearance <30ml/min)
- Morbid obesity (BMI >35 kg/m²)

4.4 Sample size calculation

A sample size of 48 patients per group is needed to provide 90% power to detect a 10-point difference in the quality of recovery score at 1 day after extubation (alpha 5%). A 10-point difference represents a minimal relevant difference (8). Based upon our previous study, the standard deviation is 15 points (9).

At the Radboudumc and LUMC, respectively 90 and 45 laparoscopic donor nephrectomies are performed annually. All eligible donors will be screened. With an inclusion rate of approximately 80%, we expect that the screening (and inclusion period) will be 11 months.

5. TREATMENT OF SUBJECTS

5.1 Investigational treatment

The patient will be randomly assigned to one of the two treatment groups (1:1):

- Deep neuromuscular block/group A
- Moderate neuromuscular block/group B

Intra-operative protocol

- induction with remifentanyl, propofol and rocuronium (intubation dose 0.6 mg/kg). Anesthesia is aimed at a bispectral index score between 45-55. Tracheal intubation is performed 2 minutes after administration of 0.6 mg/kg rocuronium in both groups. In case of a BMI > 30 kg/m² the dose rocuronium will be adjusted taking into account ideal body weight. In group A (deep NMB), an infusion of rocuronium (0.3 to 0.4 mg/kg) is started and titrated towards PTC 0-1. In group B (moderate NMB), no additional rocuronium is administered after tracheal intubation and the neuromuscular function was allowed to recover spontaneously. PTC and TOF measurements every 5 minutes.
- in case of insufficient surgical conditions due to (severe) muscle contractions (SRS 1-2), the protocol allows a 0.6 mg/kg bolus of rocuronium. In case of insufficient surgical conditions (SRS 1 or 2), the surgeon only decides to convert to an open- or hand-assisted procedure if the safety of the patient is compromised.
- pressure-regulated volume-controlled ventilation through an endotracheal tube with a mixture of oxygen in air with 5 cmH₂O PEEP and tidal volume between 6 and 8 ml/kg is used. Minute ventilation is adjusted to main end-tidal carbon dioxide between 31 and 43 mmHg by changing respiratory rate during surgery.
- neuromuscular function will be monitored in a standardized fashion by an acceleromyograph at the wrist (TOF-watch-SX, MIPM GmbH).
- blood loss will be compensated with colloid solution; for 100 ml blood loss, 120 ml colloid solution is given.
- after induction and intubation, patient is positioned in lateral decubitus position
- nasogastric tube for gastric decompression; removed before the end of surgery
- core temperature is measured continuously, aiming at 36-37 C
- no local infiltration of surgical wounds
- the use of drains is avoided
- One hour before the end of the procedure, a loading dose morphine of 0.2mg/kg will be administered.

- In group A, the rocuronium perfusor will be stopped after removal of the trocars.
- After skin closure, the NMB is reversed with sugammadex using 4 mg/kg in group A and 2mg/kg in group B. When the patients have a stable TOF ratio of more than 0.9 for 2 minutes and were fully awake, extubation is performed.

Post-operative protocol equal for all patients

- postoperative pain management: patient-controlled analgesia (morphine, 1 mg morphine per bolus, lock-out 6 minutes) and acetaminophen. On day 1 PCA morphine will be replaced by oral analgesics.
- ondansetron 4 mg intravenous (maximum 12 mg/day) or, second choice, metoclopramide (10 mg p.o.) is administered in case of nausea and/or vomiting
- removal of urine catheter on day 1
- immediate start of normal diet
- immediate mobilization

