6.5 Description and justification of route of administration and dosage

a) Rocuronium:

Rocuronium bromide is administered intravenously (i.v.) either as a bolus injection or as a continuous infusion.

The standard intubating dose during routine anaesthesia is 0.6 mg rocuronium bromide per kg body weight, which results in adequate intubation conditions within 60 seconds in nearly all patients.

If rocuronium bromide is administered by continuous infusion, it is recommended to give a loading dose of 0.6 mg rocuronium bromide per kg body weight and, when the neuromuscular block starts to recover, to start administration by infusion. In adults under intravenous anaesthesia, the infusion rate required to maintain the neuromuscular block ranges from 0.3 - 0.6 mg/kg/h. Under inhalational anaesthesia the infusion rate ranges from 0.3 - 0.4 mg/kg/h (11).

b) Sugammadex:

Sugammadex should be administered intravenously as a single bolus injection.

A dose of 4 mg/kg sugammadex is recommended if recovery has reached at least 1-2 post-tetanic counts (PTC) following rocuronium or vecuronium induced blockade.

A dose of 2 mg/kg sugammadex is recommended, if spontaneous recovery has occurred up to at least the reappearance of T₂ following rocuronium or vecuronium induced blockade (12).

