6.6 Dosages, dosage modifications and method of administration

a) Rocuronium:

In group A (deep NMB) and group B (moderate NMB), a bolus of 0.6 mg/kg rocuronium is administered intravenously before tracheal intubation. After tracheal intubation, intravenous infusion of rocuronium (0.3 to 0.4 mg/kg) is started in group A (deep NMB), when PTC is more than 0 and titrated towards PTC 0-1. In group B (moderate NMB), no additional rocuronium is administered after tracheal intubation.

b) Sugammadex:

The NMB is reversed with an intravenous bolus injection of 4 mg/kg in group A and 2 mg/kg in group B.

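### Sugammadex is dosed by arm, so a group B donor rescued late with rocuronium can be assigned 2 mg/kg where section 6.5 supports 4 mg/kg

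*Combined protocol and SAP*

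**What the plan says.** Section 5.1 sets reversal by arm: "After skin closure, the NMB is reversed with sugammadex using 4 mg/kg in group A and 2mg/kg in group B". Section 6.6, whose title includes dosage modifications, repeats these two doses and gives no exception for block depth.

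For a surgical rating scale (SRS) score of 1-2 due to muscle contractions, section 5.1 says that "the protocol allows a 0.6 mg/kg bolus of rocuronium". The bolus is not confined to one arm and has no latest time. Section 6.6 does not mention it and describes group B as receiving no rocuronium after intubation.

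Section 6.5 ties the sugammadex dose to measured recovery. For the lower dose: "A dose of 2 mg/kg sugammadex is recommended, if spontaneous recovery has occurred up to at least the reappearance of" T2. For the higher dose: "A dose of 4 mg/kg sugammadex is recommended if recovery has reached at least 1-2 post-tetanic counts (PTC").

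Three other provisions bear on the point:
- Section 5.1 requires "PTC and TOF measurements every 5 minutes".
- Section 5.1 sets the extubation rule: "When the patients have a stable TOF ratio of more than 0.9 for 2 minutes and were fully awake, extubation is performed".
- Section 6.7 says in general terms that the drugs are given in line with the product information and local routine, by an anaesthesiologist who is not blinded.

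**The concern.** The arm rule (5.1 and 6.6) and the depth rule (6.5) give the same answer in group B as long as spontaneous recovery has reached T2 by skin closure. That is what one expects after a single intubating dose and no infusion. The rescue bolus breaks the link. It is as large as the intubating dose, and group B, which has no maintenance relaxant, is where inadequate relaxation is most plausible. If the bolus comes late, the block at closure may be deeper than the 2 mg/kg dose is meant for, yet the written instruction is still 2 mg/kg.

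The participants are kidney donors. The safety argument in section 11.4 relies on sugammadex to antagonise the block at the end of surgery, which presupposes a dose suited to its depth. At stake are the safety of individual donors and the internal consistency of the dosing instructions. The efficacy analysis is not in question.

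**Working it through.** The plan gives no figure on this point, so the check is a comparison of the dosing rules.

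**Inputs**
- Assigned sugammadex: 4 mg/kg in A, 2 mg/kg in B (5.1, 6.6).
- Rescue: 0.6 mg/kg rocuronium at SRS 1-2, either arm, no time limit (5.1).
- Standard intubating dose: 0.6 mg/kg (6.5).
- Depth thresholds: 2 mg/kg from reappearance of T2, 4 mg/kg from PTC of at least 1-2 (6.5).

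**Step 1: can a rescue occur late?** Section 8.1.2 has the SRS rated after the Hasson trocar, after all trocars, and then every 15 minutes during pneumoperitoneum. A score of 1 or 2 can therefore arise near the end of that phase, and nothing in 5.1 closes the rescue option before then. Some recovery time remains between the end of pneumoperitoneum and reversal after skin closure. The documents do not say how long it is.

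**Step 2: can the bolus produce a deep block?** Rescue dose / intubating dose = 0.6 / 0.6 = 1. After that same dose at induction, section 6.6 starts the group A infusion "when PTC is more than 0 and titrated towards PTC 0-1". This implies that 0.6 mg/kg can take PTC to 0. It describes the period after intubation, so it shows only that a deep block is possible after a rescue. It does not give the depth at closure.

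**Step 3: compare the two rules in group B, by state at reversal**

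| State at reversal | 5.1 and 6.6 assign | 6.5 supports | Agree? |
|---|---|---|---|
| T2 present | 2 mg/kg | 2 mg/kg | Yes |
| T2 absent, PTC at least 1-2 | 2 mg/kg | 4 mg/kg | No |
| PTC 0 | 2 mg/kg | Neither dose | No |

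In the second row the assigned dose is 2 / 4 = 50% of the dose in 6.5.

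**Step 4: how many donors?** Number affected = group B patients × proportion rescued × proportion of those without T2 at closure. The planned group size is 48 (4.4). The documents give neither proportion, so the product cannot be evaluated. It is 0 if no one is rescued, or if every rescued donor is back to T2 by closure.

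**Step 5: what happens next?** The TOF-ratio rule keeps the patient intubated until recovery. If 2 mg/kg is not enough, the team waits or gives more. The protocol does not say which, or how much.

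**The case against.** The strongest reply is section 6.7. If administration follows the product information, and 6.5 already sets out its depth thresholds, an experienced anaesthesiologist would give 4 mg/kg to a deeply blocked group B donor. That is probably what would happen. But 6.7 is a general statement, while 5.1 and 6.6 give explicit doses by arm. Following 6.5 means departing from 5.1, and the reverse. The text does not say which governs, so the conflict stands.

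It is also fair that a recent TOF/PTC reading will be available, because measurement is required every 5 minutes. The depth check is there; only the link from reading to dose is missing. The chain of events is long and unquantified as well: poor conditions, use of an optional bolus, and late timing.

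A reader might infer more than the documents support:
- **Extubation with residual block.** The extubation rule in 5.1 excludes this as a planned outcome.
- **A measure of under-dosing from total sugammadex over total rocuronium.** Section 6.5 doses by depth, and such ratios ignore elimination, so they test nothing in the plan.
- **The same fault in group A, because its target is PTC 0-1.** Section 5.1 says "In group A, the rocuronium perfusor will be stopped after removal of the trocars", which comes before skin closure, and nothing shows that PTC is still 0 at reversal.
- **Doses going unrecorded, because 6.8 speaks only of products and batch numbers.** That section concerns drug accountability, and the case-report form is not among the documents.
- **The recurrence statement in 11.4 being refuted.** That sentence concerns slower elimination of the bound drug, not dosing after a rescue.

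**Conclusion.** The point holds, with minor severity. As written, the arm rule can assign a group B donor 2 mg/kg where the protocol's own section 6.5 supports 4 mg/kg, and this also conflicts with the general statement in 6.7. The conclusion rests on one condition: a rescue late enough that T2 is absent at skin closure. The protocol permits this but gives no basis for estimating how often it would occur.

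The consequence is slow reversal, or an extra dose without a rule, in a monitored and still intubated patient. One might suspect that the dosing gap distorts the comparison of quality of recovery. The documents do not support that: the groups are defined by regimen, analysis is by intention to treat, and the randomised comparison is not biased by this point.

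**What to change.** In sections 5.1 and 6.6, state that the sugammadex dose follows the last TOF/PTC reading before reversal, using the section 6.5 thresholds:
- Group B, T2 present: 2 mg/kg.
- Group B, T2 absent: 4 mg/kg once PTC has reached at least 1-2.
- Group A: 4 mg/kg once PTC has reached at least 1-2.
- PTC 0 in either arm: wait and re-measure.

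Name the rescue bolus in 6.6 so that it agrees with 5.1. Record each rescue bolus (dose and time), the reading at reversal and the sugammadex dose given.

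The cost is a few sentences and, if the form lacks them, a few data fields. The readings are already taken and the anaesthesiologist already knows the allocation, so blinding, sample size and analysis do not change. Donors already within the 6.5 thresholds are treated exactly as now. The downside is 2 mg/kg more sugammadex (4 − 2), or a short wait, in any patients concerned.
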